Cover Page for ClinicalTrials.gov

Official Title of the Study:

Trauma-Focused Equine-Assisted Therapy (TF-EAT) for Veterans With PTSD

NCT Number:

NCT03068325

Principal Investigator:

[name]

[contact]

[contact]

Date of Document:

February 9, 2022

Statistical Analysis Plan

The Little MCAR (missing completely at random) test on total scores for the CAPS-5, PCL-5, HDRS, and BDI-II from each time point following the baseline assessment (i.e., midpoint, posttreatment, and follow-up analysis) will be used to test whether data is missing at random.

In line with previous open-trial studies exploring novel psychotherapies for different psychopathologies, we will use an intent-to-treat analysis, thereby enabling data analysis for all 63 patients. Provided that missing data is minimal and missing at random, we will conduct the intent-to-treat analysis with full information maximum likelihood (FIML), a gold standard approach to handling missing data. In addition, we will repeat analyses for patients who complete assessments at all four time points. Treatment effects will be explored using a repeated-measures analysis of variance (ANOVA) with time (pretreatment, midpoint, posttreatment, and follow-up) as a within-subjects factor. Post hoc tests using the Bonferroni correction will be used to compare the different time points. All statistical tests will be 2-sided, using $\alpha \leq .05$. Effect sizes will be reported using η^2 and Cohen d when appropriate.

Protocol Title: **Trauma-Focused Equine-Assisted Treatment (TF-EAT) for Veterans with PTSD**

Version Date:
02/09/2022

Protocol Number:
7232

First Approval:
03/11/2016

Expiration Date:
02/21/2023

Contact Principal Investigator:
[name], PHD
Email: [contact]
[contact]

Co-Investigator(s):
[name]
[name], PHD

Research Chief:
[name]

Cover Sheet

Choose **ONE** option from the following that is applicable to your study
If you are creating a new protocol, select "I am submitting a new protocol." As 5 Year Renewals are no longer required, this option remains for historical purposes.
I am submitting an annual continuation without modifications

Department & Unaffiliated Personnel

Department

What Department does the PI belong to?
Clinical Therapeutics
Within the department, what Center or group are you affiliated with, if any?
Anxiety Disorders Clinic

Unaffiliated Personnel

List investigators, if any, who will be participating in this protocol but are not affiliated with New York

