Feedback will be gathered from participants through two methods. First, two self-report questionnaires, the Client Satisfaction Questionnaire (CSQ-8) and the Credibility/ Expectancy Questionnaire, will be administered during treatment sessions 1, 4, and 8 to ascertain whether participants feel the treatment meets their needs and if they believe it is helping to alleviate their symptoms. Second, upon completing the treatment, a researcher will interview participants to gather feedback on their overall experience in the treatment. These interviews will be audiotaped and used in combination with the CSQ-8 and Credibility/Expectancy Questionnaire to inform modifications to the treatment. Staff members will also interview therapists post treatment to gather feedback on their perceived efficacy of the intervention. These interviews will also be audiotaped and used to inform decisions on modifying the intervention.

4.A.5. Therapists and adherence to protocol:

For equine therapy, Therapists (MD or PhD level, or Masters level for social workers) will be trained and supervised weekly, by Drs. [name], [name], and [name] (consultant). Horse handlers will be trained and supervised by [name]. [name] is an equine expert with significant experience in developing EAT exercises and training horses for use in EAT. Drs. [name] will view videotapes of sessions and midway through the project make a quarterly farm visit in person to ensure adherence.

4.A.6. Termination Procedures

Drs [name], Fisher and [name], in consultation with treating clinicians, will review all currently enrolled patients in treatment in a weekly meeting. Patients may be removed from the study upon:

1. Requests to withdraw from the study.
2. Elevated level of distress, for PTSD patients demonstrated by a score of 6 or higher on the weekly CGI for two consecutive weeks, unless the distress is due to an acute transient event (to be evaluated by treating clinician, and the PI). The CGI will be administered to consider both PTSD and Depression symptomatology.
3. Non-improvement in PTSD at week 4, as measured by the CGI-I at the level of 4 (no improvement) or higher.
4. Significant suicidal ideation, as assessed by the clinician and/or by the HAM-D-Item 3 and/or the BDI suicide item and/or the CVC Suicide Risk Assessment and Screener.
5. Clear-cut deterioration in social or occupational functioning as assessed by the clinician.

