6. Non-compliance with protocol requirements.
7. New or inter-current illness that prevents the patient from complying with the protocol.

Upon termination from this study, patients may be offered alternative treatment within the Columbia Veterans Research Center (IRB #7218). Patients removed from treatment due to elevated suicide risk will be assessed by Columbia Veterans Research Center MD/PhD clinicians and provided with immediate assistance as appropriate.

You can upload charts or diagrams if any

Blood and other Biological Samples

Please create or insert a table describing the proposed collection of blood or other biological specimens
All labs will be collected under the screening protocol (IRB #7094R). A urine sample will be collected for pregnancy tests at the initial evaluation and prior to the MRI scans for female participants.

Assessment Instruments

Create a table or give a brief description of the instruments that will be used for assessment
SCID (90 minutes at screening)

Beck Depression Inventory (10 minutes)

Clinical Global Impression – Severity Scale (CGI-S) (5 minutes)

Clinical Global Impression – Change Scale (CGI-S) (5 minutes)

Clinician Administered PTSD Scale (CAPS-4) (30 Minutes)

Clinician Administered PTSD Scale (CAPS-5) (30 Minutes)

PTSD Checklist (PCL-5)

Hamilton Rating Scale for Depression (Ham-D 17) (10 minutes)

Mini Mental State Exam (MMSE)

Quality of Life (SF-12) (10 minutes)

Family Assessment Device (FAD) (15 minutes)

Client Satisfaction Questionnaire (CSQ-18/CSQ-8)

Credibility/Expectancy Questionnaire

M2C-Q

Life Events Checklist (LEC-5)

POMS

Q-LES-Q-SF

SAS

Childhood Trauma Questionnaire (CTQ) (5 minutes)

CAGE-AID Questionnaire (CAGE-AID) (5 minutes)

Columbia Veterans Center Background Information Questionnaire (5 minutes)

Columbia Veterans Center Suicide Risk Assessment and Screener (10 minutes)

Deployment Risk and Resilience Inventory (DRRI-2) (20 minutes)

Generalized Anxiety Disorder 7-Item (GAD-7) (5 minutes)

VA Traumatic Brain Injury Screening Tool (VATBIST) (5 minutes)

Anxiety Disorders Clinic Demographic and Clinical Information (5 minutes)

Traumatic Brain Injury Identification Method (TBI ID) 5 minutes

Clinician Administered Patient Treatment Log (5 minutes)

Please attach copies, unless standard instruments are used

Research Related Delay to Treatment

Will research procedures result in a delay to treatment?

Yes

Maximum duration of delay to any treatment

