MRI Scanning: MRI scanning is not associated with any known medical risks, except for persons who have a heart pacemaker or have metal in their body (e.g. shrapnel or surgical prostheses) which may be affected by the magnet. Some people have reported sensations during MRI scans with the 1.5T magnet, such as "tingling" or "twitching" (or, very rarely, a painful sensation), which are caused by changes in the magnetic field. The MRI scanner also produces a loud noise. Some subjects become anxious and feel claustrophobic in the MRI scanner. Women of child-bearing age will be required to have a pregnancy urine test at the time of medical screening and on the day of the MRI scan. For women of child-bearing age, it will also be asked and it will be documented that they responded negatively (or procedure will not occur) to questioning on the MRI day (before the procedure is initiated) whether it is possible they may have become pregnant in the prior two week period.

Describe procedures for minimizing risks

Interviews/assessments: Subjects will be informed that they may choose not to answer specific questions, and may stop the interview at any time if they are feeling uncomfortable. Trained evaluators will be sensitive to patient vulnerabilities, and every effort will be made to ensure patients' comfort.

All participants will be assessed with the HAM-D 17, and the BDI-II at intake, treatment mid-point (week 4), and end of treatment (week 8), and at a 3-month follow-up. Participants will be assessed with the BDI-II at baseline as well and with the Columbia Veterans Center Suicide Risk Assessment at intake, treatment mid-point (week 4), and end of treatment (week 8). Any indication of elevated suicide risk during treatment will prompt an immediate discussion between the clinical and therapeutic teams, and clinical evaluation. If a participant is deemed to be at greater than minimal risk at any point during treatment, the following steps will be considered:

- Provision of contact information for emergency services (911, Anxiety Disorders Clinic pager, Veterans Crisis Line, NYC Mobile Crisis Team)
- Scheduling with ADC MD as soon as possible
- Completion of Safety Plan, copy of which is kept by patient
- Discussion of removal of means, including firearms

- Removal from current protocol and enrollment within alternative treatment through the Columbia Veterans Research Center (IRB# 7218)

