MRI Scanning: Patients participating in the MRI scans will be screened by interview and questionnaire to determine the presence or absence of metallic objects, and informed that they cannot participate in the study if their body contains any paramagnetic metal other than standard dental work. Staff will be available for help and support if the subject feels anxious or claustrophobic in the MRI scanner and can stop the scan at the subject's request. To reduce noise discomfort earplugs will be provided.

Other Procedures for Minimizing Risk:

- 1) Careful medical and psychiatric screening to identify patients for whom risk for potential adverse effects are elevated. Such patients will be excluded from the study. In such cases clinicians will follow the protocol for minimizing risks during interviews and assessments described above.
- 2) Patients with any of the following will be removed from research and treated openly or as clinically indicated: a) the occurrence of assaultive or illegal behavior; b) the occurrence of active suicidal ideation at any point during the trial as assessed by clinical interview; c) behaviors while intoxicated that are a danger to self or others.
- 3) Inclusion of psychoeducation about PTSD, the treatment process and memory triggers within the therapeutic framework.

- 4) Careful monitoring of patients during pretreatment and study participation by experienced clinicians. Patients will see the same clinicians for each of their treatment visits.
- 6) Ability to remove any patient from the study who evidences significant clinical deterioration during treatment. Provisions will be made for appropriate clinical care of such patients at the Columbia Veterans Research Center (IRB #7218).
- 7) Patients failing to benefit from the study treatment will be discharged from the study and provided with appropriate clinical care based on weekly review with termination criteria
- 8) All data will be coded and stored in locked files to insure confidentiality.

Methods to Protect Confidentiality

Describe methods to protect confidentiality

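### Removal for non-improvement is optional in one section and mandatory in another, and neither provides for later assessments, so outcomes can go missing because of poor response

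*Combined protocol and SAP*

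**What the plan says.** **Protocol, 4.A.6 Termination Procedures.** The list of grounds opens "Patients may be removed from the study upon". Item 3 is "Non-improvement in PTSD at week 4, as measured by the CGI-I at the level of 4 (no improvement) or higher". The section closes by offering patients terminated from the study other treatment under a separate protocol (IRB #7218).

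**Protocol, Describe procedures for minimizing risks, Other Procedures for Minimizing Risk, item 7.** "Patients failing to benefit from the study treatment will be discharged from the study and provided with appropriate clinical care", and this is to be done "based on weekly review with termination criteria".

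**Same section, Interviews/assessments.** The HAM-D 17 and BDI-II are scheduled for all participants at intake, at mid-point, "and end of treatment (week 8), and at a 3-month follow-up". Removed patients are not mentioned.

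**Statistical Analysis Plan.** "we will use an intent-to-treat analysis, thereby enabling data analysis for all 63 patients". FIML is to be used on condition that little is missing and that it is missing at random. Little's test is run on CAPS-5, PCL-5, HDRS and BDI-II totals. The analyses are repeated in patients assessed at all four time points.

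**Application for Continuation of Research.** 71 enrolled (8 pilot, 63 trial), 64 completed; interventions are finished and only analysis continues.

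**The concern.** There are two linked difficulties.

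First, the same event, failure to improve, leads to a discretionary decision in one section and a compulsory one in the other. A reader of the results cannot tell which rule governed how long a non-improving patient stayed in treatment.

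Second, both sections take the patient out of the study rather than out of the sessions, and nothing provides for the later assessments. If the text is followed, week-8 and 3-month scores go missing because the patient was rated as responding poorly. This is a single-arm trial, so the change from baseline is the whole of the efficacy evidence, and no control arm is exposed to the same selection. The repeat analysis in patients with all four assessments drops every removed patient who has no later assessment. FIML is better placed, but it relies on an assumption that the SAP gives no means of supporting: the trigger is a CGI rating that the SAP does not name, and Little's test addresses missing completely at random, not missing at random.

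**Working it through.** **1. The plan's own figure.** 71 − 8 = 63, which reproduces the intent-to-treat population.

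**2. Ceiling on losses.** 71 − 64 = 7 non-completers: 7/71 = 9.9% overall, or 7/63 = 11.1% if all were in the trial phase. This caps removals for non-improvement only if completion means all assessments were done, and reaches the cap only if all 7 were non-improvers. The documents give no reasons for non-completion. The continuation form's answer that the investigator withdrew nobody sits under the current year's figures, a year with no new consents, so it does not settle the earlier years.

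**3. Size of the bias (assumed inputs; the documents give no effect size or SD).**
- Response u ~ N(0,1); baseline SD 9.
- Midpoint fall M = 6 + 5u + noise (SD 5); week-8 fall F = 12 + 8u + noise (SD 6).
- A share p with the worst week-4 global rating c is removed and not assessed again.
- Case A: c = u + noise (SD 0.6), so the rating carries information beyond the CAPS-5.
- Case B: c = standardized M + noise (SD 0.6), so the rating only reflects midpoint CAPS-5 change.

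Let z be the p-quantile of N(0,1), λ = φ(z)/(1 − p), δ = λ² − zλ, a_F = cov(F,c)/SD(c) and a_M = cov(M,c)/SD(c). Then:
- observed-only bias = λ·a_F;
- FIML bias (monotone normal case) = λ·(a_F − b·a_M), with b = (40 − δ·a_F·a_M)/(50 − δ·a_M²).

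At p = 7/63: z = −1.221, λ = 0.213, δ = 0.306.
- Case A: SD(c) = √1.36 = 1.166; a_F = 8/1.166 = 6.86; a_M = 5/1.166 = 4.29; b = (40 − 0.306 × 29.4)/(50 − 0.306 × 18.4) = 0.70. Observed-only bias = 0.213 × 6.86 = 1.46. FIML bias = 0.213 × (6.86 − 0.70 × 4.29) = 0.82.
- Case B: a_F = (40/7.07)/1.166 = 4.85; a_M = 7.07/1.166 = 6.06; b = 0.80. Observed-only bias = 0.213 × 4.85 = 1.03. FIML bias = 0.213 × (4.85 − 0.80 × 6.06) = 0.

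A simulation of 2,000,000 patients agrees (estimated fall, true value 12):

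| Removed | Case | FIML | FIML with week-4 rating added | Observed only |
|---|---|---|---|---|
| 9.9% | A | 12.74 | 12.01 | 13.33 |
| 9.9% | B | 12.00 | 12.00 | 12.94 |
| 11.1% | A | 12.83 | 12.01 | 13.47 |
| 11.1% | B | 12.00 | 12.00 | 13.04 |

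The FIML overstatement is therefore 0 to about 0.8 points, and the observed-only overstatement about 0.9 to 1.5. A noisier rating in case B (noise SD 1.0) lowers the observed-only figure to about 0.8 to 0.9. Adding the rating removes the FIML bias here because removal depends on nothing else. If removed patients were assessed, this bias would be absent.

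**The case against.** Much can be said for the plan.

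- *Item 7 may be only a summary.* It names neither week 4 nor the CGI and defers to the termination criteria, so it can be read as a cross-reference to 4.A.6. That narrows the conflict but does not remove it: one text permits and the other requires. A reader might infer two rival week-4 rules that fix a half course against a full course of sessions; item 7 does not go that far.
- *The outcomes may not be lost.* A reader might infer that later outcomes of non-responders are certainly missing. The documents do not say so. Removal under 4.A.6 is discretionary, the general HAM-D and BDI-II schedule excludes nobody, and one sentence in 4.A.6 speaks of removal from treatment. The text is silent on assessment after removal; it does not order that collection stop. But silence alongside discharge from the study is not a provision for follow-up, and that schedule sentence does not cover the CAPS-5 or PCL-5.
- *FIML may cope.* It does if the rating adds nothing to the modelled scores, as case B shows. The CGI is given at the same midpoint visit as the CAPS-5, so that case is plausible. Bias in the main analysis is possible, not established.
- *The loss is small.* A reader might picture 20% or 30% removed. The completion figures, on the stated reading, do not support that.
- *Treatment is over and the trial is an uncontrolled pilot.* Both are true. They limit what can be changed and how much rests on efficacy, but analysis is still open.

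**Conclusion.** The concern holds in a limited form. The optional and mandatory wordings conflict and must be reconciled; no view is taken here on which rule is right. Because both wordings end study participation and no later assessment is provided for, following the plan can make missingness depend on poor response, which sits badly with an intent-to-treat analysis of all 63.

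On the assumed inputs, with 7 removed, FIML overstates a 12-point fall by 0 to about 0.8 points (at most 0.83/12 = 7%). The observed-only mean overstates it by about 0.9 to 1.5 (at most 1.47/12 = 12%). The actual bias is unknown, because the number removed and the reasons are not reported.

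It would be wrong to conclude that the bias is beyond analysis. The unmeasured scores cannot be recovered, but the bias can be reduced with a rating scheduled at the midpoint visit. The point should be fixed; it does not overturn the design.

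**What to change.** (a) Reconcile 4.A.6 with item 7 of Other Procedures for Minimizing Risk, so that one rule covers failure to improve.

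(b) In both places, distinguish stopping treatment from withdrawing from the study. Patients who stop sessions without withdrawing consent should still be invited to the existing week-8 and 3-month assessments. With treatment finished, this serves future use of the protocol.

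(c) For the data in hand:
- include the week-4 CGI rating as an auxiliary variable in the FIML analysis;
- use any assessments obtained after removal;
- report how many patients were removed, when and why;
- describe the repeat in patients with all four assessments as exposed to this selection.

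Cost: a little more analysis work now. In any future use, up to two existing visits per removed patient, at the protocol's $100 each (at most $200). Some will decline, and later scores may reflect other care, which the Patient Treatment Log can document.
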